#### **Secondary:**

The change in mean activity during sleep between baseline phase (mean of data collected during week -1) and the final randomized treatment phase (mean of data collected during week 8), as measured by actigraphy (activity counts per minute during daily sleep period, wrist-worn accelerometer).

**Other secondary endpoints:**

The change in mean activity during sleep between baseline (mean of nights collected during week -1) and each randomized treatment and open label phase, as measured by actigraphy (week 1, 9 and 16) (activity counts per minute during daily sleep period, wrist-worn accelerometer).

The change in mean activity counts collected during the most active 30 minutes of the subject's day between baseline phase (mean of data collected each day during week -1) and each randomized treatment and open label phase (week 1, 9 and 16), as measured by wrist worn accelerometer collected actigraphy.

#### **6.4.2 Appropriateness of efficacy assessments**

Actigraphy is an appropriate and effective method for the objective measurement of physical activity in a subject's everyday life (both waking and sleeping). The sensor employed in this study, the Philips Actiwatch Spectrum, is an FDA cleared class II medical device indicated for this purpose. Assessment of both physical activity and sleep metrics using this method with this and similar devices (accelerometers) has been previously reported by other investigators. This method has been used effectively in the HF population to assess: the effect of symptom treatment on daytime activity levels ([Redfield 2015](#)), the impact of anergia on sleep and daytime activity ([Maurer 2009](#)), the effect of sleep on QoL ([Redeker 2005](#)), and physical activity patterns associated with long term survival ([Melin 2016](#)).

While polysomnography (PSG) is the standard assessment tool for sleep disordered breathing,

The Portable Monitoring Task Force of the American Academy of Sleep Medicine (AASM) recommends the use of portable monitors as an alternative to PSG for the assessment of sleep disordered breathing in patients with high pretest probability of moderate to severe sleep apnea ([Collop 2007](#)).

 A large rectangular area of the page has been completely blacked out, obscuring several paragraphs of text.

## 6.5 Safety

Safety assessments will consist of monitoring and recording of all adverse events and serious adverse events, evaluation of hematology, blood chemistry and urine values, regular measurement of vital signs and the performance of physical examinations.

### 6.5.1 Physical examination

A complete physical exam will be performed at visit number 1, 8, and 13. It will include the examination of general appearance, skin, neck, eyes, ears, nose, throat, lungs, heart, abdomen, back, lymph nodes, extremities, and vascular and neurological examinations. If indicated based on medical history, and/or symptoms, rectal, external genitalia, breast and pelvic exams will be performed.

Limited cardiovascular physical examination will be performed at visit 3 and 11, and will include the examination of vital signs (systolic and diastolic blood pressure, pulse and respiration rate), heart and lung sounds, jugular venous distension, and extremities.

Signs and symptoms of heart failure will be reviewed by the investigator at all office visits during the study. The signs and symptoms evaluation may include, but are not limited to, paroxysmal nocturnal dyspnea, fatigue, edema, dyspnea at rest, dyspnea upon effort, orthopnea, rales, jugular venous distention, presence of a third heart sound. NYHA classification will be assessed and scored at each visit.

Information for all physical examinations must be included in the source documentation at the study site. Significant findings that were present prior to the subject providing written informed consent for the study must be included in the Relevant Medical History/Current Medical Conditions eCRF. Significant findings made after the subject provides written informed consent for the study which meet the definition of an adverse event must be recorded on the Adverse Event eCRF.

### **6.5.2 Vital signs**

Vital signs will be assessed at every office visit. This will include blood pressure and pulse measurements. BP will be measured using a standard sphygmomanometer with an appropriate sized cuff and the non-dominant arm in the sitting position after 5 minutes of rest. Every effort should be made to use the same arm for the subject for all vital signs assessments and where possible, the same person doing the assessment.

### **6.5.3 Height and weight**

Height in centimeters if possible, body weight to the nearest 0.1 kg without shoes will be measured at visit 1. Body weight (to the nearest 0.1 kilogram (kg) in indoor clothing, but without shoes) will be measured at every office visit.

### **6.5.4 Angioedema**

Angioedema is a type of abrupt swelling that occurs under the skin and/or mucous membranes and is often localized to the head, neck, throat, and/or tongue, but may occur elsewhere, including the genitalia and intestines. Severe cases may be associated with airway compromise. Although, the mechanism is not fully understood, bradykinin has been implicated as the putative mediator. Therefore, medications that raise the levels of endogenous bradykinin by inhibiting the enzymes responsible for its breakdown, such as ACE, aminopeptidase P, and NEP, may result in this potentially dangerous side effect. All suspected cases of angioedema, regardless of suspected causality, must be reported. The Adjudication Questionnaire for Angioedema-like Event and Adverse Event eCRFs must be completed and the Novartis Medical Monitor must be notified.

If the angioedema event meets SAE criteria, the investigator must ensure that an SAE form is completed and submitted to Novartis Drug Safety and Epidemiology. In addition, all angioedema events will be adjudicated as described in [Section 8.5](#).

### **6.5.5 Laboratory evaluations**

A central laboratory will be used for all laboratory evaluations with the exception of the urine pregnancy test (hCG) performed at visit 1 (screening) at the site, required to determine eligibility and analysis of all collected specimens from screening through the final visit. Details on the collections, shipment of samples and reporting of results by the central laboratory will be provided to investigators in the laboratory manual.

Clinically notable laboratory findings are defined in [Appendix 1](#).

When laboratory values exceed the boundaries of a notable laboratory abnormality, additional laboratory evaluations should be performed, as judged appropriate by the investigator. If the laboratory abnormality induces clinical signs or symptoms, or requires therapeutic intervention, then the diagnosis or medical condition must be entered on the AEs screen of the subject's eCRF. If the laboratory abnormality is the primary reason for an unforeseen hospitalization or otherwise fulfills the seriousness category of an AE, then the procedure for rapid notification of SAEs must be followed. Likewise, if the laboratory abnormality leads to discontinuation from the study drug (temporarily or permanently), the subject must be followed until the abnormality resolves or until it is judged to be permanent. This investigation may include

continued monitoring by repeat laboratory testing or by performing additional laboratory tests as deemed necessary by the investigator or the Novartis medical monitor.

#### **6.5.5.1 Hematology**

Hemoglobin, hematocrit, red blood cell count, white blood cell count with differential, and platelet count will be measured at all visits: 1, 3, 5, 8, 10, and 13 (central lab).

#### **6.5.5.2 Clinical chemistry**

Blood urea nitrogen (BUN), glucose, creatinine, total bilirubin, AST (SGOT), ALT (SGPT), alkaline phosphatase, sodium, potassium, chloride, calcium, hemoglobin A1C, total protein, albumin, uric acid, and lipid profile will be measured at all visits 1, 3, 5, 8, 10, and 13 (central lab).

#### **6.5.5.3 Urinalysis**

Dipstick-test determination of specific gravity, pH, blood, total protein, bilirubin, ketones, and leukocytes will be measured at Visits 1, 3, 5, 8, 10, and 13 (central lab). If dipstick is positive, a qualitative microscopic determination, including white blood cells high power field (WBCs/HPF) and red blood cells high power field (RBCs/HPF) will be performed.

[figure not shown]
### **6.5.6 Pregnancy and assessments of fertility**

[figure not shown]
All female subjects of childbearing potential will have a urine pregnancy test (hCG) performed at Visit 1 (site). In addition, these subjects will have a serum pregnancy test performed at visits 3, 6, 8, 11 and 13 (central lab). If any of these tests are positive, the subject must be discontinued from the study.

### **6.5.7 Appropriateness of safety measurements**

The majority of safety assessments selected for this study are standard for this indication/subject population. They include the monitoring and recording of all adverse events and serious adverse events, evaluation of hematology, blood chemistry and urine, regular measurements of vital signs and the performance of physical examinations.

### **6.6 Other assessments**

#### **6.6.4 Sensor Measurements**

There are two wearable sensor systems that will be used for measurement:

[figure not shown]
##### **Actiwatch**

- Wrist worn activity and light monitor using the Philips Actiwatch (waterproof) (Philips Respiration, Boston MA): This device is a 510k registered class 2 medical device indicated to: “collect and score data for sleep parameters and assess activity in any instance where quantifiable analysis of physical motion is desired”.
  - This device will be worn on the non-dominant wrist of the subject, day and night for the entire study duration from the time of enrollment (start of the 2 week baseline phase) to the end of the open-label extension phase (treatment week 16). This device uses an accelerometer to monitor the occurrence and degree of sensor motion which is captured in ‘counts’ (0.000175 G-force per activity count). Data from the accelerometer will be sampled at a frequency of 32 Hz and stored in 30 second data epochs. Data from the sensor will be uploaded from the Actiwatch to Philips data collection system during assessment periods, which will be scored by Philips and will be blinded to treatment. For the purpose of endpoint determination, onset of sleep will be defined by 10 consecutive motionless (< 40 counts/min) 1-minute intervals and waking will be determined by 10 consecutive intervals of activity (< 40 counts/min). Sleep onset and awakening times will be confirmed by a Philips technician, over-read and verified to align with typical sleep wake times and ambient light sensor data.

- Actiwatch data captured during the baseline phase is crucial. If a subject is not compliant (not wearing the Actiwatch more than 3 days or less than half of the 2 week baseline phase), they will be asked to repeat the 2 week baseline phase. After randomization, subjects who refuse to wear the device will be discontinued; subjects who have an unintentional lapse of compliance will be asked to immediately resume wearing the device.
- During visit 1, subjects will be trained on the Philips Actiwatch. The Actiwatch will be exchanged and data uploaded by the site at visit 3, 6, 8, 11 and 13.

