## **2 Study objectives and endpoints**

[figure not shown]
Measurements will be done at weeks -1, 1, 8, 9, and 16. Week 8 is considered the primary time point (end of double blind period).

[figure not shown]

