#### **3.1      Study design**

This study is a multicenter, randomized, double-blind, double dummy, parallel group, active-controlled 8-week study with open label extension using medical device-grade subject worn sensors to measure waking and sleeping physical activity in the ambulatory outpatient setting. The 18 week study duration will consist of a 2-week baseline observation phase (with subjects continuing their current heart failure drug therapy), followed by an 8 week blinded treatment phase during which subjects are randomized (1:1) to either initiation of sacubitril/valsartan treatment or enalapril comparator, and finally an 8 week open label extension phase during which all subjects are treated with sacubitril/valsartan. Each subject will undergo a 36 hour washout period [during which ACEi (Angiotensin converting enzyme inhibitor), or study drug will be withheld] before the start of the randomized, blinded treatment phase, and again before beginning the open label extension phase. The study will include 8 office visits and 5 tele-visits.

Subjects will wear a wrist-worn actigraphy device continuously for the 18 week duration of the study, from the time of enrollment (the start of the 2 week baseline phase) to the end of the open-label extension phase (end of treatment week 16). During this 18 week interval, the devices will be exchanged five times during five study visits, to guard against data loss and ensure adequate battery life. Data will be collected continuously during the trial and although only data collected during assessment periods will contribute to prospectively defined endpoints, other data may be assessed in future analysis of patterns observed during the study. Additionally, continuous wear reduces opportunities for lapses in compliance while adding very minimal assessment burden for subjects.

Each assessment period is seven contiguous days. This will allow for continuous actigraphy recording over the seven day period.

**Figure 3-1** Study design

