### 3.2 Rationale for study design

The design of the study facilitates the assessment of change in sequential daily physical activity, [REDACTED] HF symptoms and health-related quality of life; between baseline to select time point assessment periods after randomized, blinded assignment to treatment with sacubitril/valsartan versus the active comparator enalapril. Assessment of the primary endpoint at 8 weeks captures the early impact of initiation of sacubitril/valsartan versus enalapril, which is the focus of the study.

Waking activity will be the primary endpoint, and sleep activity (a measure of sleep disturbance) is the secondary endpoint. Actigraphy, which has been well characterized for the measurement of both daytime and sleep physical activity variables, will be used to inform the primary and secondary endpoints.

[figure not shown]
Prior to randomization, there will be a 2 week phase where device familiarization and baseline assessment will be completed. The initial baseline week will provide an opportunity for the subjects to become familiar and acclimated to the testing devices and assessment routines, prior to entering the baseline phase of the study. Data from the second week of this phase, the 'baseline phase' (Week -1) will be considered as the baseline value for comparison to subsequent periods. Data collected outside of the defined measurement periods will be excluded from analysis for the defined study endpoints.

The 36-hour wash-out interval after randomization and before entering the open-label extension is required per the FDA approved USPI label because there is a potential for increased risk for angioedema in subjects who receive both an ACE inhibitor and the combination of sacubitril/valsartan.

The randomized comparison phase of 8 weeks provides the direct assessment of the initial and early changes associated with sacubitril/valsartan treatment to treatment with the active comparator enalapril.

The open label phase of 8 weeks provides the opportunity for every subject to receive sacubitril /valsartan. This results in one group of subjects that will receive sacubitril/valsartan for a total of 16 weeks, providing information on the endpoints after this duration of continuous therapy. It also provides the opportunity to evaluate changes after initiating sacubitril/valsartan in a group of subjects who all had been previously receiving enalapril treatment for 8 weeks.

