**Table 5-5 Study drug dispensed during double-blind treatment epoch**

Visit	Dose Level	SacubitriI/valsartan**	Enalapril	Route	Timing
Rando/Visit 3	1 a,b	24/26 mg or matching placebo BID	2.5 mg or matching placebo BID	Oral	AM & PM
Week 2/Visit 5	2 c/d	49/51 mg / 97/103 mg or matching placebo BID	5 mg or matching placebo BID	Oral	AM & PM
Week 4/Visit 6	2 c/d	49/51 mg / 97/103 mg or matching placebo BID	10 mg or matching placebo BID	Oral	AM & PM

\*\*Investigational product labeling for sacubitriI/valsartan dose levels is based on the total contribution of both components of sacubitriI/valsartan and reads, 50 mg, 100 mg and 200 mg. This is equivalent to the sacubitriI/valsartan dose levels 24/26 mg, 49/51 mg and 97/103 mg, respectively.

a. Initial starting dose (Level 1) Eligible patients will be randomized via IRT to either sacubitriI/valsartan or enalapril, Dose Level 1.

b. Available after Rando/Visit 3 to end of double-blind treatment epoch only if Dose Levels 2 and 3 are not tolerated despite modification of other non-disease-modifying HF medications and re-challenge.

c. Only if Dose Level 3 is not tolerated despite modification of other non-disease-modifying HF medications and re-challenge.

d. This target Dose Level must be maintained for as long a duration as possible. If down-titration is necessary due to side effects, the patient should be re-challenged as soon as medically possible per the investigator's judgment.

- At Randomization on Day 1 (Visit 3, enrolled subjects will be randomized via IRT to either sacubitriI/valsartan or enalapril. All subjects will start at Dose Level 1 (2.5 mg enalapril or 24/26 mg sacubitriI/valsartan, BID).
- At Week 1 (Visit 4), subjects will have a telephone visit.
- At Week 2 (Visit 5), subjects will be force-titrated to the next dose, Dose Level 2 (5 mg enalapril or 49/51 mg sacubitriI/valsartan, BID) or Dose Level 3 (10 mg enalapril or 97/103 mg sacubitriI/valsartan, BID) and remain on this dose through the evening dose prior to Week 4 (Visit 6).
- At Week 4 (Visit 6), subjects will be force-titrated to the next dose, Dose Level 2 (5 mg enalapril or 49/51 mg sacubitriI/valsartan, BID) or Dose Level 3 (10 mg enalapril or 97/103 mg sacubitriI/valsartan, BID) and remain on this dose through the evening dose prior to Week 8 (Visit 8).
- At Week 6 (Visit 7), subjects will have a telephone visit.

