### **5.6.2 Discontinuation of study treatment**

Subjects may voluntarily discontinue the study drug for any reason at any time.

Study drug must be discontinued under the following circumstances:

- Withdrawal of consent
- Pregnancy
- Use of prohibited concomitant medication
- Any protocol deviation that constitutes a risk to the subject
- Investigator believes that continuation of study drug may be detrimental to the subject's well-being
- Study medication may be discontinued at the investigator's discretion if any of the following occur:
  - Any severe suspected drug related AE
  - Suspected occurrence of angioedema. A subject with any signs or symptoms of clinically significant angioedema should be thoroughly evaluated by the investigator to determine if it constitutes a reason for discontinuation of study medication.

Depending on the serum potassium, blood pressure, or eGFR, subjects may need to have their study drug dose or the dose of another concomitant medication reduced or discontinued; or, if appropriate, have potentially contributing agents adjusted. Refer to appendices for treatment guidelines for hyperkalemia, hypotension or renal dysfunction, respectively.

In the case of study drug discontinuation, every effort must be made to complete an end of study visit and obtain follow up health status information for any subjects that withdraw from the

study. If the subject refuses, he/she should be contacted by telephone in place of protocol-specified visits unless the subject expressly refuses such contacts.

The investigator must notify the sponsor of any study drug discontinuation and record it on the Dosage Administration Record eCRF.

If discontinuation of study treatment occurs, the subject should NOT be considered withdrawn from the study. The subject should return to the clinic as soon as possible, after discontinuation of study drug, for an end of study visit. All assessments from the final visit (Visit 13) in the visit schedule of assessments ([Table 6-1](#)) must be completed and recorded in the eCRF. The Study Completion eCRF will also need to be completed. The investigator must determine the primary reason for the subject's premature discontinuation of study treatment and record this information in the eCRF.

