#### **9.4.3 Handling of missing values/censoring/discontinuations**

Missing data will be imputed using the last-observation-carried-forward (LOCF) method. If a subject has no post-baseline value, the missing value will not be imputed and the subject will be removed from the analysis. If a subject's data is missing or unevaluable for the week preceding randomization, the data from the previous week will be used as the baseline measurement. If a subject's data is missing or unevaluable for each of these weeks, the subject will be excluded from the analysis.

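### Protocol 6.6.4 discontinues any randomized subject who refuses the watch, in any week; for a refusal confined to Weeks 2-7 this gives up a Week 8 recording that might still have been obtained (minor, cheap to fix)

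*Protocol*

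**What the plan says.** The Actiwatch text in Protocol 6.6.4 separates two situations after randomization. An unintentional lapse leads only to a request to put the watch back on. Refusal is handled differently: "After randomization, subjects who refuse to wear the device will be discontinued". The text sets no week limit, offers no chance to resume, and does not say whether discontinuation is from study drug or from the study.

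Protocol 5.6.2 describes what follows when study drug stops: "The subject should return to the clinic as soon as possible, after discontinuation of study drug, for an end of study visit". The Visit 13 assessments and the Study Completion eCRF are completed at that point. The same section adds: "If discontinuation of study treatment occurs, the subject should NOT be considered withdrawn from the study". Subjects who do not attend visits are followed by telephone. Watch refusal is not among the circumstances listed there in which study drug must stop.

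On which recordings count, Protocol 2 says: "Measurements will be done at weeks -1, 1, 8, 9, and 16". Protocol 3.1 says that "only data collected during assessment periods will contribute to prospectively defined endpoints", and Protocol 3.2 confirms it: "Data collected outside of the defined measurement periods will be excluded from analysis for the defined study endpoints". For a missing Week 8 value, Protocol 9.4.3 says: "Missing data will be imputed using the last-observation-carried-forward (LOCF) method". SAP 2.5.3 repeats that rule, and SAP 2.5.1 requires at least five days of data for a weekly mean.

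**The concern.** The watch is worn continuously, but the randomized phase has only two post-baseline assessment weeks, Week 1 and Week 8. Someone who takes the watch off in Week 3 and would put it on again in Week 7 has lost nothing that the primary analysis uses. It is the discontinuation rule that turns this temporary refusal into a missing Week 8 value.

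What replaces that value is a poor substitute. Week 1 is the only earlier post-baseline assessment, and it precedes the first up-titration at Week 2: "All subjects will start at Dose Level 1". If Week 1 has fewer than five valid days, there is nothing to carry forward and the subject leaves the analysis. At stake is a small amount of avoidable missing primary data. If the word is read as stopping study drug, randomized treatment also ends for a measurement reason.

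**Working it through.** **Sequence for a refusal confined to Weeks 2-7**

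1. Weeks 2-7 contain no assessment period (Protocol 2, 3.1, 3.2), so the refusal alone costs no defined-endpoint data.
2. Protocol 6.6.4 discontinues the subject. If this means study drug, 5.6.2 brings an early end-of-study visit, with telephone contact for those who do not attend. If it means the study, follow-up stops. Neither reading plans a Week 8 recording.
3. LOCF then has only Week 1 to carry. The dose at Week 1 is 50/200 = 25% of target for sacubitril/valsartan (total-component labelling) and 2.5/10 = 25% for enalapril.
4. If Week 1 is not valid, the subject is removed (Protocol 9.4.3, SAP 2.5.1 and 2.5.3).

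**The plan's own sample size.** Inputs from Protocol 9.8 and 9: difference 5000, SD 7400, two-sided 0.05, 90% power, 20% drop-out plus 10% non-evaluable.

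- n per arm = 2(1.96 + 1.2816)² × (7400/5000)² = 46.03, so 47 (48 with the t distribution).
- Total = 2 × 47/0.70 = 134.3, so 135 (138 with t). The plan states 136.
- At 136 × 0.70 = 95.2 evaluable, or 47.6 per arm, power is 90.9% (90.4% with t). The plan's figure is reproduced.

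**Size of the effect.** The documents give no refusal or resumption rate, so all of the following is assumption.

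- Refusers in Weeks 2-7, if 1%, 4% or 8% of 136 refuse, spread evenly over eight weeks: 136 × 0.01 × 6/8 = 1.0; 136 × 0.04 × 6/8 = 4.1; 136 × 0.08 × 6/8 = 8.2.
- Analysed number if LOCF keeps drop-outs and 10% are non-evaluable: 136 × 0.9 = 122.
- Loss in expected difference, with refusers split evenly between arms = refusers × fraction who would resume × share of effect absent at Week 1 × 5000/122.

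| Refusers, Weeks 2-7 | Would resume | Effect absent at Week 1 | Loss (counts) | Share of 5000 |
|---|---|---|---|---|
| 1 | 0.5 | 0.5 | 10 | 0.2% |
| 4 | 0.5 | 0.5 | 41 | 0.8% |
| 8 | 0.5 | 0.5 | 82 | 1.6% |
| 8 | 1 | 1 | 328 | 6.6% |

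The last row is a ceiling. With the smaller base of 95.2, the first three rows become 0.3%, 1.1% and 2.1% (for example 4 × 0.25/95.2 = 1.1%).

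**Power on the plan's own base** (47.6 per arm, normal approximation, SD unchanged), if a given share of analysed subjects carries Week 1 forward and 0-50% of the effect is present at Week 1:

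- 1%: difference 4950-4975, power 90.4-90.7%.
- 2%: difference 4900-4950, power 89.8-90.4%.
- 5%: difference 4750-4875, power 87.9-89.5%.

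The 5% case needs about five subjects (0.05 × 95.2 = 4.8) who refuse in Weeks 2-7 and would all have resumed.

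**The case against.** The best defence is that the rule will seldom apply. Refusal most naturally means settled unwillingness, since lapses are already handled by a request to resume, and a settled refuser loses Week 8 under any rule. Exclusion criteria 4 and 5 and the two weeks of wear before randomization screen for this. Protocol 3.1 gives a reason for continuous wear: fewer lapses for little burden. All of that stands, and it limits the point to the few who would have resumed.

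Two further points also stand. Carrying Week 1 forward is a general feature of LOCF, which this fix does not change. And Protocol 3.2 sets aside a week of acclimation before baseline, so a subject who puts the watch on only for Week 8 would be compared with a better-acclimated baseline.

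A reader might infer more than the documents support:

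- *That the rule breaches the intent-to-treat principle.* The statement in Protocol 9.1 concerns analysis by assigned arm. A discontinued refuser stays in the FAS in that arm and is analysed by LOCF if Week 1 is valid.
- *That such discontinuations would be hidden.* SAP 2.3.1 has categories for patient and physician decision and plans disposition listings, and Protocol 5.6.2 requires the primary reason to be recorded.
- *That power can be read off at 61 per arm (122/2).* That would credit drop-outs carried forward by LOCF with the full 5000-count effect while discounting only refusers, so I give no power figure on that base.

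**Conclusion.** The point holds as a minor, inexpensive improvement. For a refusal confined to Weeks 2-7, the rule rather than the refusal removes the planned Week 8 recording. A subject who would have resumed is then represented by a Week 1, Dose Level 1 value or drops out of the analysis.

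The effect on the expected difference is probably well under 2%. That judgement rests on few refusers (about four or fewer), only some of whom would resume, and on part of the effect being present at Week 1. The last assumption is consistent with the anecdotal early improvement cited in Protocol 1.1. None of these inputs is in the documents. It would be tempting to call the rule a threat to the primary result; the documents give no basis for that. Nor do they say categorically that a refuser is withdrawn from the study: the wording is unclear, but no reading of it plans a Week 8 recording.

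**What to change.** Replace the refusal sentence in Protocol 6.6.4 with text such as:

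> After randomization, a subject who declines to wear the device is not discontinued from study treatment or from the study for that reason alone. The subject stays on the visit schedule and keeps the device or is reissued one, at an unscheduled visit if needed. The site records the start and stop dates of refusal and asks the subject to resume, where possible some days before Week 8 to allow re-acclimation, and to wear the device throughout the Week 8, Week 9 and Week 16 assessment periods.

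Continuous wear remains the expectation. The reissue clause matters because, in Table 6-1, the only scheduled contact between the watch exchanges at Visit 6 (Day 28) and Visit 8 (Day 56) is the telephone call at Visit 7. Protocol 6 already permits unscheduled visits.

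The cost is one amended sentence, a place to record refusal dates, and an occasional extra visit. The downsides are a few subjects followed on treatment without actigraphy and, for those who resume late, possibly a less acclimated Week 8 recording.
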